## Research Determination

1. \* Select one of the following that applies to the project

- Research Project or Clinical Investigation
- Exception from Informed Consent for Planned Emergency Research
- Humanitarian Use of Device for Treatment or Diagnosis
- Humanitarian Use of Device for Clinical Investigation
- Emergency Use of Investigational Drug, Biologic or Device
- Treatment Use (Expanded Access to Investigational Product for Treatment Use)
- Center or Institute Administrative Grant Review

2. \* VCU requires that all clinical research studies be evaluated to determine if a Coverage Analysis is required. Has your study been evaluated by your school/center's Research Administration Office

- Yes
- No
- Not Applicable

\*\*\*If No above, please contact the appropriate office about completing required coverage analysis documentation for your study.  
(School of Medicine [[contact]](mailto:[contact]) Other Schools/Colleges [CRSADM [contact]](mailto:CRSADM [contact]))

## Federal Regulations

1. \* Is this a Clinical Trial? A clinical trial is a study that prospectively assigns human subject(s) to an intervention(s) and evaluates the effects of the intervention on health-related outcomes

- Yes
- No

2. If Other IRB, name the IRB that will review this research. If ORSP has not already agreed to rely on this IRB (via phone or email communication), you are strongly advised to contact [contact] before proceeding with this submission

ID: HM20011025

View: SF - Review Setup

## Review Setup

1. \* Does this study involve greater than minimal risk

- Yes  
 No

2. \* Review Type Requested (subject to IRB approval)

- Full Board  
 Expedited  
 Exempt

3. \* Has this protocol received a Massey protocol review

- Yes  
 No

4. \* Has this human subjects protocol (not the grant application) been reviewed by the funder

- Yes  
 No

ID: HM20011025

View: SF - Research Description

## Research Description

1. \* Describe the study hypothesis and/or research questions. Use lay language whenever possible.

Primers are a type of 'glue' routinely used in orthodontics to attach brackets (metallic components) to the teeth. OpalSeal is a fluoride-releasing primer that has the potential to reduce cavities in patients receiving braces.

Orthodontic patients are at particular risk of developing two types of early carious lesions (decay):

- Around the brackets called White Spot Lesions and
- Along the sides of the teeth after slenderization procedure called inter-proximal reduction (IPR).

Our research questions are:

- Can OpalSeal offer protection against white spot lesions (WSL) around the brackets?
- Can OpalSeal offer protection against decay on the sides of teeth following IPR?

2. \* Describe the study's specific aims or goals. Use lay language whenever possible.

We know that fluoride is very effective in preventing dental decay (cavities) when applied in the form of a varnish on tooth surfaces.

The purpose of this study is to verify if fluoride-releasing primer (OpalSeal) offers more protection against early dental decay (cavity) compared to conventional primer (Transbond XT) during treatment with braces.

3. \* Describe the study's background and significance, including citations, or upload a citation list in document upload. Use lay language whenever possible.

Plaque is a sticky, colorless film of bacteria that constantly forms on our teeth that ferments sugars from diet to produce acids. These acids have been shown to dissolve enamel (outermost layer of tooth) that eventually forms a cavity. Having braces increases plaque build up and food accumulation around the brackets (1-2, 4-7), resulting in increased risk for dental decay (cavities).

The formation of white spot lesions (WSL) is a common risk in patients who undergo orthodontic treatment (1-4), especially those with poor oral hygiene practices (5). The prevalence ranges from 50-96%. WSL represent the early stages of caries (1,3,4) and can form within 4 weeks of the start of treatment (7). The lesions appear white, chalky, and opaque and can make the end result of orthodontic therapy very unaesthetic (3,6).

Fluoride application on the surfaces of teeth has been shown to effectively increase the resistance of enamel to acid attack and reduce decay. Fluoride is currently delivered in a variety of ways: varnishes, gels and mouthrinses (8-11). Fluoride varnish, applied by a dental professional, has been very effective in caries prevention and a similar strategy to deliver fluoride around brackets can potentially prevent WSL.

The process of gluing brackets onto a tooth involves application of a primer followed by a resin. Conventional primers do not have fluoride and one such primer (Transbond XT) is routinely used in our patients receiving braces in the Department of Orthodontics. Opal Seal is a recently introduced primer that contains fluoride and has the potential of reducing the incidence of WSL.

OpalSeal has been approved for clinical use by the FDA and does not present any known risks.

A recent animal study has shown that Opal Seal significantly reduced the erosive attack of acidic beverages (12).

PR is a routine procedure employed by orthodontists to treat patients with mild to moderate crowding. IPR is actually a slenderization process that involves abrading away little layers of outermost tooth enamel from the sides of the teeth using hand-held, flexible, diamond-coated abrasive strips. The amount of enamel that we would remove as part of this study is (up to) twice the width of human hair from each side of the tooth.

PR does not require anesthesia and can be accomplished within 15 minutes. Even though some studies have shown no long term adverse effects of IPR (13,14), others have shown increased plaque accumulation potentially increasing the risk of developing a cavity (15, 16). Our research is interested in evaluating if applying OpalSeal following PR would offer any benefit following IPR.

(Refer to citation list for numbered references)

4. \* Describe the proposed research using language understandable to those IRB committee members whose expertise is not scientific. The description must include

- A statement explaining the study design
- A detailed description of all the procedures that will be followed to carry out the study, preferably in sequential order
- A description of all research measures/tests/interventions that will be used (if applicable)
- A detailed description or list of all secondary data elements and/or secondary specimens that will be obtained and how they will be used (if applicable)

See the help text for additional guidance.

Patients at the VCU Orthodontic clinic, 10 years and older, who have consented to for orthodontic treatment (braces) that involves extraction of at least 2 teeth (one on the right and the other on the left side of the mouth) will be approached for participation in the study. Interested participants will be recruited to the study following informed consent process. Dental extraction of teeth as part of orthodontic treatment is typically referred to an oral surgeon and it takes approximately three months to get this procedure. The standard clinical practice in the Department of Orthodontics is to begin treatment right away without waiting for extractions.

Since the teeth planned for extraction are on either side of the mouth, we will use a split-mouth design with random assignments for interventions (OpalSeal). Apart from the intervention, patients will be treated the same way they would be if they were not participating in research. All patients will be given oral hygiene instructions and they will have no additional appointments for research purposes.

Study related interventions will be restricted to teeth that are planned for extraction and will not involve other teeth. These interventions include:

1. Bonding brackets on to-be-extracted teeth, with one receiving OpalSeal
2. Selective grinding of enamel ( PR) on to-be-extracted teeth, with one tooth receiving OpalSeal
3. Collection of extracted teeth for laboratory analysis
4. Completion of a short survey

The patient will schedule the extraction appointment with the dentist of their choice (routine clinical protocol) and will update the Orthodontic clinic. Typically, the patients come to the clinic a day or two prior to extraction to get the wires removed (dentists will not extract the teeth with wires still on). At this time, the patient will be given labeled plastic jars containing water and will be instructed to collect the teeth after extractions. The corresponding dentist will be instructed to place the teeth in the jars and hand over the container to the patient. As is the regular protocol, patients will report to the Orthodontic clinic within a few days of extractions to have the wires replaced and continue treatment. Study personnel will collect the jars containing extracted teeth at this follow up appointment.

All specimens will be transferred into 0.1% thymol solution (disinfectant) and stored until analysis. There will be no personally identifiable information on the jars. Samples will undergo the following tests:

- a. Scanning electron microscopy to analyze the surface topography
- b. Micro-CT to quantify the mineral density
- c. Atomic force microscopy to test surface roughness and hardness
- d. Fluorescence to quantify the residual amount of OpalSeal

The survey will help us understand how the patient controlled factors affect the incidence of WSL. For example, are right-handed patients more likely to develop WSL on the right side?

"The statistician will generate and provide a computer generated random assignment table to the resident [REDACTED]. The resident will be the only person that will be providing the interventions (OpalSeal or TransbondXT) to the study participants."

1. Bonding brackets on to-be-extracted teeth: Placing brackets on teeth are fundamental to moving teeth and teeth will have a bracket attached at the start of treatment. However, teeth planned for extractions do not receive any brackets in routine clinical practice. In our study though, we will place brackets even on to-be-extracted teeth until they are extracted. Since every patient will have at least two teeth that would be extracted, one of them would receive OpalSeal while the other will receive Transbond XT. The procedures for bonding will be consistent with clinical procedures and protocol for any orthodontic patient treated in the clinic.
2. Administering OpalSeal: OpalSeal will be applied to the teeth of interest following manufacturer's instructions for use (refer to the attached document).
3. Selective grinding of enamel ( PR) on to-be-extracted teeth: PR is a deliberate procedure performed on selected teeth to relieve crowding. As a clinical routine, IPR is not done on teeth that are planned for extraction. In our study though, we will do PR on to-be-extracted teeth. Since every patient will have at least two teeth that would be extracted, one will receive OpalSeal after IPR while the other will receive Transbond XT. The PR procedure will involve using a handheld diamond-coated abrasive strips and will use routine diagnostic radiographs to guide the amount of enamel that is shaved off or removed. The procedure will not require any anesthesia and can be accomplished in a few minutes. The amount of enamel removed during this research specific intervention will be similar to what is routinely done in clinical practice, which would be approximately 200 um from two sides of the teeth for all study participants.
4. Completion of a short survey: We would like to have a formal structure to collect pertinent information that can give insights about the effectiveness of OpalSeal to prevent early carious lesions given patient's risk factors. This is not a requirement for required for routine clinical practice. The resident will administer the survey once the patient/parent signs the informed consent document. It will be a paper format and all completed surveys will be stored in the PIs office in a locked cabinet. If the patient has some difficulty in completing the survey, parent's/resident's help will be solicited."

5. Upload any supporting tables or documents (e.g. protocol documents, figures/tables, data collection forms, study communications/reminders)

ID: HM20011025

View: SF - Study Activities

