## Sample Collection

1. \* Select all of the types of samples that will be collected as part of this study

- Amniotic Fluid
- Blood
- Buccal Smears
- Saliva
- Tissue
- Urine
- Other
- None of the Above

2. If Other, please describe the type of sample being collected

1. Teeth extracted at the time of extraction

3. \* Describe how the samples will be collected and the collection schedule. For each type of sample, include information about

- The procedures that will be followed to collect the sample
- The role(s) of the individuals who will collect the sample
- The volume/size range of the sample
- The timing and frequency of sample collection

Conventional Clinical Protocol:

Patients who require extractions will be referred to an oral surgeon (of their choice) for extraction of teeth. Patients will report to the clinic with the dates of scheduled extractions (with dentists' name and contact information) and they will be seen in the clinic for removal of wires and brackets (from the two teeth that would be extracted). The surgeon cannot remove teeth if the brackets and wires are still in place.

Within a few days after extractions, the patients will report to the clinic for putting the wires back. This way there is minimal disruption to the orthodontic treatment.

For study participants:

When these patients report to the clinic for removal of wires, they will be handed 2 screw-capped plastic jars containing water, clearly labeled right or left for collecting right or left sided teeth. In addition, these jars will also have the initially-assigned, study code, so that the dentist and the patient are blinded to which tooth had OpalSeal. This will not have any PHI that will identify the tooth to the patient by any non-study personnel. The patients will be instructed to hand over the jars to the office staff at the time of extraction. At the end of extraction appointment, the patient will collect the jars (with teeth) and take it home. They will hand over the jars containing the teeth when they return to the clinic to put the wires back on.

The PI can and will independently verify which tooth had OpalSeal when the samples arrive at the laboratory. This additional step will ensure the collected data is robust and valid.

4. \* Will Genetic Testing be conducted on any of the samples

- Yes  
 No

5. \* Will any of the samples be used for a pregnancy test

- Yes  
 No

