**See the help text for additional guidance.**

All signed informed consent documents and completed surveys will be stored in a locked cabinet in the PI's office. The extracted teeth will be collected in jars containing no PHI from the oral surgery clinic and will be stored in a refrigerator in locked laboratory (Dental Materials Laboratory, Wood Building 101) until analysis.

In our study, every patient will serve as his/her own control. This is because every patient will have two teeth extracted, one of which will receive OpalSeal and the other, Transbond XT. We will use a computer generated random number table to determine which tooth will receive OpalSeal or Transbond XT. We will generate a code based on:

- order of patient enrollment and
- whether the tooth received OpalSeal (e) or Transbond XT (c)
- date of tooth extraction

2. This key that links code to the patient will be stored in the PI's office computer that has restricted access (only to study personnel).

3. The key will be destroyed when the extracted teeth are collected from the patient. Since we would not be needing any PHI, this would decrease the risk of loss of confidentiality.

2. \* Who will have access to study data

PI, co-investigator, student researcher, and statistician will have access to the study data. They are all part of the study team.

3. \* If the study will code (i.e. de-identify) the research data by replacing subjects' names with assigned subject IDs, explain the following aspects of the coding process

1. The process for how subject IDs will be generated/assigned (e.g. random, sequential)

2. Whether there will be a key that links the subject ID with direct identifiers.

If a key will be created, describe

3. The place where the key will be stored

4. The role(s) of all individuals who will have access to the key

5. When the key will be destroyed

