**See the help text for additional guidance.**

The statistician will provide the study team with the computer generated random table. The study participants will be sequentially assigned a 3-digit code followed by R or L (for Right or Left) for OpalSeal. For example, patient 1 may be 001R. The key to the code will be kept by the PI in a password-protected computer and will be destroyed at the end of study.

We will have 2 codes to simplify the process and decrease confusion:

The jars handed over to the patients will have fields for date; patient initials; tooth number; Right or Left sides. Patient will be given these jars and will be instructed to hand this over to the staff at the oral surgery clinic who will place the extracted teeth in the correct containers.

Once the patient hands over the containers (with extracted teeth) to the Orthodontic Clinic, the teeth will be transferred to another jar with the original study codes. The resident and or members of the study team will collect the jars containing the teeth directly from the participant.

4. \* Will the sponsor or investigator obtain a certificate of confidentiality for this study

- No - CoC will not be Obtained
- Yes - CoC has been Obtained
- Yes - CoC Request is Pending
- Yes - Plan to Submit CoC Request

5. If the Certificate of Confidentiality has been obtained by the PI, upload it here

6. \* What will happen to the research records when the research has been completed

- Stored indefinitely with identifiers removed
- Stored indefinitely with identifiers attached
- Destroyed at the end of study once the minimum time required for data retention has been met per VCU Data Retention Policy and/or sponsor retention requirements
- Destroyed when notified by sponsor but not less than the minimum time required for data retention per VCU Data Retention Policy
- Other

7. If Other, explain

8. If "stored indefinitely with identifiers attached", explain why identifiers are necessary

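### The full random assignment table goes to the resident who applies both primers and to the study team, so the OpalSeal side can be known before the study teeth are chosen and prepared

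*Protocol*

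**What the plan says.** On allocation, Research Description, item 4, states: "The statistician will generate and provide a computer generated random assignment table to the resident". It continues: "The resident will be the only person that will be providing the interventions (OpalSeal or TransbondXT) to the study participants". Data Confidentiality and Storage, item 3, widens the circle: "The statistician will provide the study team with the computer generated random table". The code is described there too: "The study participants will be sequentially assigned a 3-digit code followed by R or L (for Right or Left) for OpalSeal". The example given is 001R.

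On tooth preparation, Research Description, item 4, has enamel removed with hand-held strips, to about 200 um, with radiographs guiding the amount. For the primer that goes with this step, "one will receive OpalSeal after IPR while the other will receive Transbond XT". The lists in item 4 put bonding of brackets before IPR but do not say that this is the chairside order.

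On blinding, the Placebo/No Treatment section relies on blinded participants and random assignment. Sample Collection, item 3, adds the extracting dentist: "these jars will also have the initially-assigned, study code, so that the dentist and the patient are blinded to which tooth had OpalSeal". Nothing describes keeping the side from the person who prepares the teeth.

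**The concern.** What is randomized is which of two teeth in one mouth receives OpalSeal. The comparison is fair only if the two teeth are chosen and prepared without regard to that assignment. A person who holds the whole table and sees patients numbered in sequence can read the next side before touching either tooth.

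If one tooth of a pair were then stripped or prepared differently, even unintentionally, the result could not be told apart from an OpalSeal effect. Surface topography, mineral density, roughness and hardness are all measured on these teeth after extraction. The difference would lie between the two teeth of a pair, so comparing within patients would carry it into the estimate.

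**Working it through.** No arithmetic applies. The check sets the statements side by side.

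1. **Who holds the table.** The resident (Research Description, item 4) and the study team (Data Confidentiality and Storage, item 3). The second statement stands by itself, so the words blacked out after the first do not matter.

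2. **What it reveals.** Codes run in order of enrollment and end in the OpalSeal side. Table and sequence together show the next patient's side.

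3. **When it is known.** The handover is not dated, and no envelopes, central release or other stepwise disclosure are described. Giving the table to the person who must apply the primers most naturally means before treatment, but that is an inference.

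4. **Which steps are open to it.**
   - *Choice of the pair.* Study Population, item 4, requires at least two extractions, so a choice can arise only where there are more than two. The number of such patients is not given.
   - *IPR.* The primer used at this step follows the stripping. The target of about 200 um applies to all participants, which limits variation. But the amount is approximate, guided by radiographs and removed by hand. Risks, item 2, also has a safe thickness identified from x-rays beforehand, so some judgement remains.
   - *Preparation for bonding.* This follows routine clinic procedure and leaves less room.

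5. **How the order of procedures matters.** One letter per patient implies that the same side serves both steps.

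| Existing order | Protected by release just before the first primer | Not protected |
|---|---|---|
| IPR first | Pair choice; IPR on both teeth, if release waits for it | Anything done after the first primer |
| Bonding first | Pair choice; preparation for bonding | The later IPR |

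6. **Extent.** Study Population, item 1, gives 35 participants, hence up to 35 allocations. The power statement for 30 patients in item 3 concerns white spot lesion scores and does not measure this exposure.

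7. **The code on the jars.** Sample Collection, item 3, puts the initially assigned code on the patients' jars as the means of blinding. Data Confidentiality and Storage, item 1, builds the treatment into the code (e or c), and item 3 builds in the OpalSeal side. Yet item 3 also says: "The jars handed over to the patients will have fields for date; patient initials; tooth number; Right or Left sides". The teeth are moved to jars with the study code later, and Existing Data/Specimen Details, item 3, agrees. Sample Collection is therefore the outlier. If its jars carried a code that bears the treatment, the label could show what it is meant to hide.

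**The case against.** The strongest reply is that the split-mouth design leaves little to exploit. Every patient receives both primers, so foreknowledge cannot steer patients between them. The teeth largely follow from the treatment plan, one on each side, and the IPR target is common to all. All of this stands and narrows the point to unequal handling within a pair and, in some patients, choice of the pair.

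A second reply is that late release may miss the step with most operator judgement. If bonding comes first, the operator knows the side before IPR whatever the envelope does. This also stands, so the protocol must state the order and admit that limit.

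A reader might go further in three ways that the document does not support:
- That the operator certainly knew the side beforehand. The timing is not stated.
- That the teeth were or will be prepared unequally, or that the trial is invalid. The text shows only that the side can be known.
- That the jar labels bias tooth preparation. The jars are handed out when the wires come off, typically a day or two before extraction and after both primers have been applied.

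The Risks section says that experienced specialists perform the procedures, so someone other than the resident may do IPR. This changes little, because the study team also receives the table.

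**Conclusion.** The point holds as a limited weakness in allocation concealment. It is more than a missing detail, because handing over the whole table is a stated procedure. The OpalSeal side can be known when the pair is chosen, where more than two teeth are extracted, and when the teeth are prepared, including IPR if it precedes the first primer.

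The conclusion assumes that the table arrives before treatment and that no unstated stepwise release exists. Up to 35 allocations are covered, but the size and direction of any bias cannot be derived from the document. The design stands. This is an inexpensive improvement that should be made, because unequal preparation cannot be corrected once the teeth are extracted. The conflict over the jar code is real but secondary.

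**What to change.** 1. In Research Description, item 4, and Data Confidentiality and Storage, item 3, have the statistician keep the table. Release each patient's side by sequentially numbered, sealed, opaque envelope, or one at a time on request. Open it only after the study pair is recorded and immediately before the first primer is applied, and after IPR on both teeth if IPR comes first in the existing order. The operator necessarily sees the side from then on.

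2. State the existing order of bonding and IPR; no change of order is asked for. If bonding comes first, acknowledge that the envelope protects the choice of pair and the preparation for bonding but not the later IPR.

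3. Secondary: use a plain 3-digit number as the study code until the envelope is opened, and on anything the extracting dentist or the patient sees. The jars keep right or left to identify the tooth. Reconcile Sample Collection, item 3, with Existing Data/Specimen Details, item 3, and Data Confidentiality and Storage, items 1 and 3, on which code the patients' jars carry.

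The cost is about 35 envelopes, a brief chairside step and text edits. The sample size does not change and no patient procedure is added.
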